4.8.3 Analysis of Pharmacokinetics

Serum concentrations of nirsevimab at selected time points will be evaluated to confirm that adequate exposures are maintained after dosing. Nirsevimab serum concentration data will be presented in descriptive statistics. Serum PK parameters such as C_{max} , T_{max} , and AUC_{0-150} will be estimated using noncompartmental analysis and summarized with descriptive statistics. The estimated PK parameters from the adult Chinese subjects from this study will be compared for similarity with those obtained from non-Chinese adult subjects from the global Phase 1a Study D5290C00001. This PK comparison will be presented separately from the clinical study report. Notably, regression-dependent PK parameters such as $t_{1/2}$ and apparent systemic clearance will not be estimated due to the limited sampling up to 150 days which would require at least 40% extrapolation of the total $AUC_{0-\infty}$. Nonetheless, the predictability and consistency of the PK properties of nirsevimab as demonstrated in 102 adults in the Phase 1a Study D5290C00001 and 984 infants in the Phase 1b/2a Study D5290C00002 and Phase 2b Study D5290C00003 support the hypothesis that the apparent clearance and other regression-dependent PK parameters should be similar if the C_{max} , T_{max} , and AUC_{0-150} are shown to be similar.

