1.4.1 Phase 1a Study D5290C00001

Study D5290C00001 was a first-time-in-human Phase 1a, randomized, double-blind, placebo-controlled, dose-escalation study conducted to evaluate the safety, tolerability, PK, and ADA of nirsevimab compared to placebo in healthy adult volunteers (Griffin et al 2017). This study was completed in June 2015. A total of 136 subjects were randomized and received a single fixed dose of nirsevimab (6 subjects each at doses of 300 mg IV, 1000 mg IV, 3000 mg IV, 100 mg IM, and 78 subjects at 300 mg IM) or placebo (34 subjects). All subjects were followed for approximately 360 days after dosing.

Safety

The safety profile of nirsevimab was favorable, with similar proportions of treatment-emergent adverse events (TEAEs) reported in the placebo (61.8%) group and the nirsevimab (62.7%) total group. Two treatment-emergent serious adverse events (TESAEs; gunshot wound and appendicitis) were reported in 2 nirsevimab subjects. TEAEs judged to be related to investigational product were reported in 29.4% of subjects in the placebo group, and 17.6% of subjects in the nirsevimab total group. The most frequent TEAEs in the nirsevimab total group included upper respiratory tract infection (URTI; 18.6%); headache (8.8%); urinary tract infection (5.9%); and dermatitis contact, musculoskeletal pain, nausea, and vomiting (4.9% each). The most frequently occurring TEAEs in the placebo group were headache (17.6%); URTI (8.8%); and nausea, increased blood creatine phosphokinase level, and paresthesia (5.9% each). There were no adverse events of special interest (AESIs) or new onset chronic diseases (NOCDs). There were no deaths. No safety signals in this healthy adult population were observed. These results demonstrated an acceptable safety profile for nirsevimab, including no observed hypersensitivity reactions, and supported further clinical studies of IM administration of 1 dose of nirsevimab in the target population of infants to provide protection for the duration of the RSV season.

Pharmacokinetics

A 2-compartment PK model adequately described the PK profile following both IV and IM administrations. Body weight was determined to be a significant covariate on systemic clearance and volume of distribution with allometric exponents. The mean population

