clearance and volume of distribution were 42.3 mL/day and 2.8 L, respectively. The mean $t_{1/2}$ of nirsevimab ranged from 85 to 117 days across dose groups, and bioavailability after IM administration was 77%. The predicted 3- to 4-fold increase in the $t_{1/2}$ of nirsevimab compared to a standard IgG antibody was confirmed.

Antidrug Antibody

Post-baseline ADA was detected in 13.7% of subjects in the nirsevimab total group and 15.2% of subjects in the placebo group, with a maximum titer of 1:800 and 1:400, respectively. On Day 361, ADA was detected in 5.3% of nirsevimab subjects and 10.7% of placebo subjects. The highest titer at Day 361 was 1:200 for both the nirsevimab and placebo groups. The presence and titer of ADA had no effect on the PK or safety profiles.

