3.1 Description of the Study

3.1.1 Overview

Study D5290C00007 is a Phase 1, randomized, double-blind, placebo-controlled study to evaluate the PK, safety, and tolerability of nirsevimab compared to placebo when administered as a single fixed IM dose of 300 mg to healthy Chinese adult subjects. Enrollment is planned at a single study center in China.

Approximately 24 subjects will be randomly assigned in a 3:1 ratio to receive nirsevimab (n = 18) or placebo (n = 6). All subjects will be followed for approximately 150 days after dosing to assess safety, PK, and ADA response.

Figure 1 Study Flow Diagram

ADA = antidrug antibody; IM = intramuscular; PK = pharmacokinetics.

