4.1.2 Inclusion Criteria

Subjects must meet all of the following criteria:

- 1 Age 18 to 45 years, inclusive, at the time of screening.

- 2 Written informed consent and any locally required authorization obtained from the subject prior to performing any protocol-related procedures, including screening evaluations.
- 3 Females of childbearing potential who are sexually active with a nonsterilized male partner must have used at least 1 highly effective method of contraception (see [Appendix A](#) for definition of females of childbearing potential and for a description of highly effective methods of contraception) from screening and must agree to continue using such precautions for 150 days after receipt of the dose of investigational product. It is strongly recommended for the male partner of a female subject to also use a male condom plus spermicide throughout this period. Cessation of contraception after this point should be discussed with a responsible physician. Periodic abstinence, the rhythm method, and the withdrawal method are not acceptable methods of contraception.
 - (a) Females not of childbearing potential who are either permanently sterilized (hysterectomy, bilateral oophorectomy, or bilateral salpingectomy) or postmenopausal. Women < 50 years of age will be considered postmenopausal if they have been amenorrheic for ≥ 12 months prior to the planned date of randomization without an alternative medical cause and have follicle-stimulating hormone levels in the postmenopausal range.
- 4 Nonsterilized male subjects who are sexually active with a female partner of childbearing potential must use a male condom with spermicide from Day 1 (the day of investigational product administration) through 150 days after receipt of the dose of investigational product. It is strongly recommended for the female partner of a male subject to also use a highly effective method of contraception throughout this period, as described in [Appendix A](#). In addition, male subjects must refrain from sperm donation while on study and for 150 days after the final dose of investigational product.
- 5 Weight ≥ 45 kg and ≤ 110 kg and body mass index of 19 to 26 kg/m² at screening.
- 6 Healthy Chinese subjects (both male and female) based on medical history, physical examination, vital signs, and laboratory tests, as determined by the Investigator.
- 7 Normotensive (defined as systolic blood pressure < 140 mm Hg and diastolic blood pressure < 90 mm Hg).

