4.8.2 Sample Size

This study will randomize approximately 24 subjects of whom approximately 18 will receive nirsevimab and approximately 6 will receive placebo. Because all analyses will be descriptive in nature and no hypothesis is being tested statistically, no formal sample size calculation was performed. Current sample size and sampling scheme are selected to facilitate estimation and numerical comparison of C_{max} , time to maximum observed concentration (T_{max}), and area under the concentration-time curve from time 0 to 150 days (AUC_{0-150}) between Chinese and non-Chinese adult subjects.

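### The protocol specifies no account of body weight in the cross-study PK comparison, although the sponsor's Phase 1a model found weight a significant covariate on clearance and volume

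*Supplement*

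**What the plan says.** The primary hypothesis (section 1.7.1) is that the PK profile over 150 days in Chinese subjects resembles that in subjects of other racial and ethnic backgrounds. No hypothesis is tested formally. Section 4.8.3 addresses it by a cross-study comparison: the PK parameters "will be estimated using noncompartmental analysis and summarized with descriptive statistics", and they "will be compared for similarity with those obtained from non-Chinese adult subjects from the global Phase 1a Study D5290C00001". Section 4.8.2 calls the comparison numerical and says all analyses are descriptive. Section 4.8.3 adds: "This PK comparison will be presented separately from the clinical study report".

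On body weight, the protocol contains the following.

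- Section 1.4.1, on the Phase 1a model: "Body weight was determined to be a significant covariate on systemic clearance and volume of distribution with allometric exponents". That model covered IV and IM doses together. The exponents are not given.
- Section 3.1.1: nirsevimab is evaluated "when administered as a single fixed IM dose of 300 mg to healthy Chinese adult subjects". Phase 1a also had a fixed 300 mg IM group, of 78 subjects.
- Section 4.1.2, criterion 5: weight 45 to 110 kg and "body mass index of 19 to 26" kg/m².
- Table 4: weight is measured at screening.

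None of the synopsis, sections 3.2.2 and 3.2.3, or sections 4.8.2 and 4.8.3 mentions weight adjustment, normalisation, matching, a weight-stratified summary or a pooled population model for the comparison.

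**The concern.** At a common fixed dose, a lighter subject is expected to have higher exposure if clearance and volume rise with weight. Two studies that differ in mean weight would then differ in Cmax and AUC0-150 with no ethnic effect at all. An unadjusted ratio mixes body size with ethnicity. It can suggest dissimilarity where there is none, or look close to 1 because a weight effect and an ethnic effect cancel.

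The results are meant to support registration in China (section 1.5) for an infant indication in which the proposed dose depends on weight band in the first season (section 3.2.1). A weight gap between two adult samples says little about infants. An effect beyond weight is the more useful finding, and the unadjusted ratio does not isolate it. The protocol also states no similarity margin that would limit how the ratio is read.

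**Working it through.** The protocol states no sample-size calculation, margin or power, so there is no planned figure to reproduce.

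**1. Are the protocol's PK inputs coherent?** Section 1.4.1 says population "clearance and volume of distribution were 42.3 mL/day and 2.8 L, respectively", and gives IM bioavailability as 77%.

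AUC0-∞ = F × dose / CL = 0.77 × 300 mg / 42.3 mL/day = 5,461 µg·day/mL.

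Table 3 gives an observed median of 4,917 for 300 mg IM, so the ratio is 5,461 / 4,917 = 1.11. A mean-based value set against a median makes this broadly coherent. Exposure at the fixed dose varies inversely with apparent clearance.

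**2. Ratio due to weight alone.** If clearance is proportional to weight to the power b, the Chinese/non-Chinese ratio of AUC0-∞ with no ethnic effect is (W_ref / W_Chinese)^b. Both b and the mean weights are assumptions.

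| Mean weight, Chinese vs reference | b = 0.5 | b = 0.75 | b = 1.0 |
|---|---|---|---|
| equal | 1.00 | 1.00 | 1.00 |
| 65 vs 70 kg | 1.04 | 1.06 | 1.08 |
| 65 vs 75 kg | 1.07 | 1.11 | 1.15 |
| 60 vs 80 kg | 1.15 | 1.24 | 1.33 |

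**3. Does this carry over to the planned parameters?** A one-compartment simplification was used, with assumed absorption rate 0.4/day, half-life 85 or 117 days (the ends of the Phase 1a range), and assumed exponents of 0.75 for clearance and 1 for volume.

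- 65 vs 75 kg: Cmax ratio 1.15, AUC0-150 ratio 1.13 to 1.14.
- 60 vs 80 kg: Cmax ratio 1.33, AUC0-150 ratio 1.29 to 1.30.

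**4. Random error of the ratio.** The inputs are 18 subjects here and at most 78 in Phase 1a; the number who are non-Chinese is not stated. The CV is assumed to be 23% to 35%. The only AUC CV printed is 35%, for AUC0-∞ in Phase 2b infants.

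- Log-scale SD: s = √ln(1 + CV²) = 0.227 to 0.340.
- 90% half-width: 1.661 × s × √(1/18 + 1/78) = 0.099 to 0.148.
- On the ratio scale this is a factor of 1.10 to 1.16.

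A 5 kg gap (1.04-1.08) stays inside this error. A 10 kg gap (1.07-1.15) can match it. A 20 kg gap (1.15-1.33) exceeds it over most of the assumed range.

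**5. Masking (b = 0.75, AUC0-∞).**

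- True Chinese CL/F 10% higher, 65 vs 75 kg: (75/65)^0.75 / 1.10 = 1.01.
- True CL/F 20% higher, 60 vs 80 kg: (80/60)^0.75 / 1.20 = 1.03.

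Both ratios sit close to 1 despite a real difference in clearance.

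**The case against.** The strongest reply is that silence is not a decision. Section 4.8.1 leaves further detail to the SAP, which was not among the documents reviewed, and the comparison will appear in a separate report. A reader might infer that the sponsor has chosen to ignore weight. The documents do not support that: they show only that the protocol specifies no account of it. This limits the claim but does not remove it. The protocol does commit to a method (noncompartmental, descriptive, numerical), and section 3.2.3 argues that Cmax, Tmax and AUC0-150 alone are enough. A comparison reported outside the study report may also fall outside the study SAP.

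A reader might also infer from the BMI cap that this sample is lighter than Phase 1a. The cap does restrict weight here: 26 × 1.70² = 75 kg at 1.70 m, and 110 kg would need a height of √(110/26) = 2.06 m. The Phase 1a limits and weights are not given, however, so the cap shows no difference between the studies.

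Two further objections stand. Section 1.4.1 calls weight a significant covariate in a model of IV and IM doses together; it gives no effect size and nothing specific to 300 mg IM. Confirming that adequate concentrations are maintained, another stated purpose in sections 3.2.3 and 4.8.3, uses observed values and needs no adjustment. Observed exposure at a fixed dose and exposure net of body size answer different questions, so the adjusted ratio belongs beside the unadjusted one, not in its place.

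That the analysis is descriptive is a weaker reply, since a descriptive ratio is confounded in the same way as a tested one.

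**Conclusion.** The point holds at protocol level. The comparison that bears on the primary hypothesis specifies no account of a covariate that the sponsor's own model found significant, at a fixed dose common to both groups. A difference in mean weight could look like an ethnic difference or hide one.

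That such a bias will occur, or that it has a particular size, does not follow from the documents. The ratios of 1.04 to 1.33 rest on assumed exponents (0.5-1.0) and assumed mean weight gaps of 5 to 20 kg, and with equal mean weights there would be almost no bias. The error of ±10% to ±16% rests on an assumed CV and on 78 comparators as an upper limit. The point is a low-cost improvement to the comparison. It does not show that the planned result would be wrong.

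**What to change.** In section 4.8.3, and in whichever document governs the separate comparison, specify the following before the PK data are seen:

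1. Summarise body weight in both studies.
2. Report the unadjusted geometric mean ratio for Cmax and AUC0-150 and, beside it, a weight-adjusted ratio with its confidence interval. Obtain the adjusted ratio by regressing the log parameter on study and log body weight.
3. Use as comparator the non-Chinese Phase 1a subjects given 300 mg IM, and state their number.
4. If the weight distributions overlap little, the regression relies on extrapolation. In that case add an analysis using the weight terms of the existing two-compartment model. This is supporting evidence and not an equivalent analysis, because it estimates different quantities under different assumptions.

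The cost is about a paragraph of text and one small regression per parameter. Weight is already collected at screening and Phase 1a is complete, so no subjects, samples or visits are added.

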This study will randomize approximately 24 subjects of whom approximately 18 will receive nirsevimab and approximately 6 will receive placebo. Because all analyses will be descriptive in nature and no hypothesis is being tested statistically, no formal sample size calculation was performed. Current sample size and sampling scheme are selected to facilitate estimation and numerical comparison of C_{max} , T_{max} , and AUC_{0-150} between Chinese and non-Chinese adult subjects.

Pharmacokinetic Analyses

Serum concentrations of nirsevimab at selected time points will be evaluated to confirm that adequate exposures are maintained after dosing. Nirsevimab serum concentration data will be presented in descriptive statistics. Serum PK parameters such as C_{max} , T_{max} , and AUC_{0-150} will be estimated using noncompartmental analysis and summarized with descriptive statistics. The estimated PK parameters from the adult Chinese subjects from this study will be compared for similarity with those obtained from non-Chinese adult subjects from the global Phase 1a Study D5290C00001. Notably, regression-dependent PK parameters such as $t_{1/2}$ and apparent systemic clearance will not be estimated due to the limited sampling up to 150 days which would require at least 40% extrapolation of the total area under the concentration-time curve from time 0 to infinity. Nonetheless, the predictability and consistency of the PK properties of nirsevimab, as demonstrated in 102 adults in the Phase 1a Study D5290C00001 and 984 infants in the Phase 1b/2a Study D5290C00002 and Phase 2b Study D5290C00003, support the hypothesis that the apparent clearance and other regression-dependent PK parameters should be similar if the C_{max} , T_{max} , and AUC_{0-150} are shown to be similar.

Safety Analyses

All TEAEs will be summarized overall and by Medical Dictionary for Regulatory Activities (MedDRA) system organ class and preferred term, severity, and relationship to investigational product. In addition, summaries of deaths and TESAEs will be provided. Other safety assessments will include the occurrence of AESIs defined as adverse events of anaphylaxis and other serious hypersensitivity reactions, including immune complex disease (eg, vasculitis, endocarditis, neuritis, glomerulonephritis), or thrombocytopenia following investigational product administration, and the occurrence of NOCDs following investigational product administration.

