There was no impact of the presence of ADA on safety. ADAs did not appear to impact PK for 150 days after dosing, but there may have been an impact between Day 151 and Day 361.

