3.2.3 Rationale for Endpoints

Serum concentration of nirsevimab at selected time points will be evaluated as the primary endpoint to confirm that adequate serum exposures are maintained at least 5 months after dosing (ie, through Day 151; duration of a typical RSV season). The estimated PK parameters from the adult Chinese subjects in this study will be compared for similarity with those obtained from non-Chinese adult subjects from the global Phase 1a Study D5290C00001.

Nirsevimab being a mAb with a half-life extending YTE modification has a predictable linear PK profile across a range of doses studied both in adults and infants. Also, it does not have any internal targets; thus, it does not go through any target-mediated clearances to have the potential to alter the PK profile past the 150 days from the injection. Therefore, the 150-day PK profile comparison based on only C_{max} , t_{max} , and AUC_{0-150} assures the similarity of efficacious exposures as well as provides the opportunity to confirm the safety.

ADA will be measured at selected time points throughout the study up to Day 151.

Safety endpoints include TEAEs, TESAEs, AESIs (defined as hypersensitivity including anaphylaxis, immune complex disease, and thrombocytopenia), and NOCDs.

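### The 40% extrapolation floor does not follow from the stated half-lives, and similar Cmax, Tmax and AUC0-150 are weak evidence of similar clearance

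*Supplement*

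**What the plan says.** Section 4.8.3 estimates Cmax, Tmax and AUC0-150 by noncompartmental analysis and compares them with non-Chinese adults from Phase 1a Study D5290C00001. It omits half-life and apparent clearance because sampling ends at 150 days, "which would require at least 40% extrapolation of the total" AUC0-∞. The synopsis gives the same reason: "require at least 40% extrapolation of the total area under the concentration-time curve". No derivation is shown.

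Section 4.8.3 then argues from earlier PK experience that "apparent clearance and other regression-dependent PK parameters should be similar if the" three retained metrics are shown to be similar. Section 3.2.3 supports this with linear kinetics and the absence of an internal target. It rests the 150-day comparison on *only* Cmax, Tmax and AUC0-150. Section 4.8.2 names the same three metrics as the basis of the Chinese versus non-Chinese comparison.

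The adult kinetics are in Section 1.4.1. The mean half-life "of nirsevimab ranged from 85 to 117 days across dose groups", IM bioavailability was 77%, and mean population "clearance and volume of distribution were 42.3 mL/day and 2.8 L, respectively", from a two-compartment model. No half-life is given for the 300 mg IM group alone. Table 6 schedules the last PK sample at Day 151 (±10 days).

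**The concern.** There are two linked problems.

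- A stated minimum should hold across the half-lives the protocol reports. Here the 40% looks like a value from the upper end of that range, yet it is the only reason given for omitting half-life and clearance.
- The text then recovers those parameters by inference from three metrics that respond weakly to clearance. Cmax is set mainly by dose, bioavailability and volume. Tmax is set mainly by absorption. AUC0-150 cuts off the part of the curve where clearance shows most.

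The results are meant to support registration in China, and the comparison has no similarity margin. A reader could take similar Cmax, Tmax and AUC0-150 as evidence of similar clearance when a moderate difference would fit the same data.

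**Working it through.** **Inputs from the protocol.** Half-life 85–117 days, bioavailability 77%, clearance 42.3 mL/day, volume 2.8 L (1.4.1); horizon T = 150 days (4.8.3); 18 nirsevimab subjects (4.8.2); 78 Phase 1a subjects at 300 mg IM (1.4.1).

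**Step 1: can the 40% be reproduced?** For mono-exponential decline the share of AUC0-∞ beyond T is x = exp(−ln2 × T / t½).

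- 85 days: exp(−1.223) = 29.4%
- 101 days (midpoint): 35.7%
- 117 days: exp(−0.889) = 41.1%
- Half-life needed for 40%: 150 × ln2 / ln(1/0.4) = 113.5 days

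First-order absorption with an assumed Tmax of 3–14 days gives 29.6–42.0%, and the half-life needed for 40% becomes 110.7–113.1 days. Two-compartment versions use clearance 42.3 mL/day, central volume 2.8 L and assumed peripheral values. They give 28.9% (half-life 83 days) to 40.0% (114 days). The visit window also matters: with a last sample at 140 days the mono-exponential threshold falls to 106 days, and at 160 days it rises to 121 days.

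Reading 42.3 mL/day and 2.8 L as one compartment would give a half-life of 46 days and about 10%. That is not a fair test, because the model has two compartments. I do not use it.

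So 40% lies near the top of the range, not at its floor.

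**Step 2: how strongly do the metrics respond to clearance?** Hold volume and absorption fixed and multiply clearance by r. Without absorption:

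- AUC0-150 ratio = (1 − x^r) / [r(1 − x)]
- concentration ratio at 150 days = x^(r−1)
- AUC0-∞ ratio = 1/r

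For r = 1.3:

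- x = 0.294: AUC0-150 ratio = (1 − 0.204) / (1.3 × 0.706) = 0.87; concentration ratio = 0.294^0.3 = 0.69
- x = 0.411: AUC0-150 ratio = (1 − 0.315) / (1.3 × 0.589) = 0.89; concentration ratio = 0.411^0.3 = 0.77

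The ranges below cover a one-compartment model with absorption (Tmax 6 days assumed) and the two-compartment versions (absorption rate 0.35/day assumed).

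| Metric | Clearance ×1.3 | Clearance ×1.5 |
|---|---|---|
| Cmax | 0.985–0.992 | 0.976–0.987 |
| Tmax | 0.95–0.98 | 0.92–0.97 |
| AUC0-150 | 0.87–0.90 | 0.79–0.84 |
| Day 151 concentration | 0.69–0.77 | 0.54–0.64 |
| AUC0-∞ | 0.77 | 0.67 |

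The elasticities with respect to clearance (log change per log change, one-compartment) are −0.03 to −0.04 for Cmax, about −0.2 for Tmax, −0.38 to −0.49 for AUC0-150, −0.9 to −1.2 for the Day 151 concentration, and −1 for AUC0-∞. A 5% shift in a Tmax of 6 days is 0.05 × 6 = 0.3 day. Sampling on Days 2, 4, 6, 8 and 15 cannot resolve that.

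**Step 3: precision.** The adult CV of AUC0-150 is not given, so I assume 20–35%. The upper value is the infant AUC0-∞ figure in 1.4.3. With 18 versus 78 subjects the standard error of the log ratio is √ln(1 + CV²) × √(1/18 + 1/78). The 90% interval is then the ratio multiplied and divided by 1.09 to 1.16. A 30% clearance difference, seen through AUC0-150, would be detected at two-sided 5% with about 24–78% power.

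**The case against.** The defence has real substance, and several stronger conclusions that a reader might draw do not hold.

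- *That the 40% is wrong.* The reported half-lives are means across IV and IM groups, and the 300 mg IM value is missing. A value of about 111–113.5 days or more lies inside the range and would give 40%. Even 30% is a substantial extrapolation, so omitting noncompartmental half-life and clearance can be defended either way.
- *That AUC0-150 barely responds to clearance, so the inference fails.* Its response is attenuated, not absent: 50% higher clearance lowers it by 16–21%. Cmax and AUC0-150 together carry some information on clearance. The protocol also words the inference as a hypothesis backed by prior consistency and linearity, not as a decision rule.
- *That low late exposure would go unseen.* Serum concentrations through Day 151 belong to the primary endpoint and will be summarised within the trial. The gap is only that Day 151 is not named in the cross-study comparison.
- *That antidrug antibodies undercut Section 3.2.3.* Section 1.4.2 does say "there may have been an impact between Day 151 and Day 361". That remark is tentative, concerns preterm infants, and comes with no apparent effect on PK for the first 150 days. Sections 1.4.1 and 1.4.3 report no PK effect in adults or in Phase 2b. The sentence in 3.2.3, "it does not go through any target-mediated clearances to have the potential to alter the PK profile past the 150 days", is about target-mediated clearance.

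Details are left to an analysis plan that is not among the documents, and the PK comparison is to be reported separately from the study report. Either may already include a late-concentration comparison. That does not change the protocol's own wording, which names three metrics and says *only*.

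**Conclusion.** The point holds as a correction of wording and a modest gap in the comparison. From 85–117 days the extrapolated share is about 29–42%, so *at least 40%* is unsupported as a minimum unless the 300 mg IM half-life is shown to be about 111–113.5 days or longer.

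The inference to clearance is weaker than its wording suggests. Two of the three metrics are nearly blind to clearance, and the third shows about 40–50% of a difference on the log scale. A 30% clearance difference would appear as a 10–13% fall in AUC0-150, which with 18 subjects and no margin could be read as similar. The same difference lowers the Day 151 concentration by 23–31%.

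These sizes assume volume, bioavailability and absorption unchanged, the absorption and peripheral values stated above, and an adult CV of 20–35%. The primary endpoint, sampling schedule and sample size are not called into question.

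**What to change.** 1. In Section 4.8.3 and the synopsis, restate the extrapolation as about 30–42% for half-lives of 85–117 days (the range with absorption), or cite the 300 mg IM half-life that yields 40%.
2. Delete the sentence inferring similar clearance and half-life, or qualify it by saying that AUC0-150 is at most about half as sensitive to clearance as AUC0-∞. Remove *only* from Section 3.2.3.
3. Add the Day 151 concentration to the Chinese versus non-Chinese comparison as a geometric mean ratio with a confidence interval. The Phase 1a sampling days are not given. If none falls near Day 151, use a model-based value for that study. Show actual sampling times, because ten days within the window moves the concentration by 6–8% (2^(10/117) = 1.06; 2^(10/85) = 1.08).

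The cost is a wording change and one more row in a comparison already planned. If Phase 1a lacks a sample near Day 151, there is also some modelling. No new visits or samples are needed. A pooled population-model fit and a count above the paediatric 6.8 µg/mL target are optional and not needed to close this point.
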